5.1.2 Modified Intention-to-Treat (mITT) Populations

Sensitivity analyses of SVR₁₂ as described in Section 10.5 will be performed on the ITT population modified to exclude subjects who did not achieve SVR₁₂ for reasons other than virologic failure (mITT-VF).

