The presence of baseline polymorphisms in NS3 and/or NS5A did not have an impact on SVR₁₂ rates for GT1-, 2-, 4-, 5-, or 6-infected subjects.

Within GT3-infected subjects, baseline polymorphisms in NS3 did not have an impact on treatment outcome. The NS5A polymorphisms at positions 24, 28, 31, 58, 92, or 93 (including Y93H) did not have an impact on treatment outcome, whereas the A30K polymorphism was associated with a slightly decreased SVR₁₂ rate. Given the low prevalence of A30K (6.3%; 39/615) and that the majority of subjects with A30K achieved SVR₁₂, its impact on overall SVR is expected to be minimal.

Amino Acid Substitutions in Subjects Experiencing Virologic Failure

Among TN and TE-PRS subjects without cirrhosis or with compensated cirrhosis treated for 8, 12, or 16 weeks, 23 subjects experienced virologic failure (2 with GT1, 2 with GT2, and 19 with GT3). A GT3-infected subject experiencing virologic failure was determined to have been reinfected with GT3a virus distinct from the one present at baseline.

Therefore, baseline polymorphisms and treatment-emergent substitutions were analyzed for 22 subjects experiencing virologic failure.

Among the 2 GT1-infected subjects, 1 had treatment-emergent substitutions A156V in NS3 and Q30R/L31M/H58D in NS5A, and 1 had treatment-emergent Q30R/H58D (while Y93N was present at baseline and post-treatment) in NS5A.

Among the 2 GT2-infected subjects, no treatment-emergent substitutions were observed in NS3 or NS5A; the prevalent M31 polymorphism in NS5A was present at baseline and post-treatment in both subjects.

Among the 18 GT3-infected subjects, the majority of subjects had treatment-emergent substitutions at the time of failure in NS3 (61.1%, 11/18) and NS5A (88.9%, 16/18). Treatment emergent NS3 substitutions Y56H/N, Q80K/R, A156G, and Q168L/R were observed in 11 subjects, and A166S or Q168R was present at both baseline and post-treatment in 5 subjects. Treatment-emergent NS5A substitutions M28G, A30G/K, L31F, P58T, or Y93H were observed in 16 subjects, and 13 subjects had A30K (n = 9) or Y93H (n = 5) at both baseline and post-treatment.

Integrated Safety Results

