SVR₄ = HCV RNA < LLOQ in the SVR₄ window (4 weeks after the last actual dose of active study drug) without any confirmed quantifiable (\geq LLOQ) post-treatment value before or during that SVR window.

SVR₁₂ = HCV RNA < LLOQ in the SVR₁₂ window (12 weeks after the last actual dose of active study drug) without any confirmed quantifiable (\geq LLOQ) post-treatment value before or during that SVR window.

Relapse₁₂ = confirmed HCV RNA \geq LLOQ between end of treatment and 12 weeks after last actual dose of active study drug (up to and including the SVR₁₂ window) for a subject with HCV RNA < LLOQ at Final Treatment Visit who completed treatment (as defined below), excluding HCV reinfection as described below.

Relapse_{overall} = confirmed HCV RNA \geq LLOQ between end of treatment and up to and including the last HCV RNA measurement collected in the Post-Treatment Period for a subject with HCV RNA < LLOQ at Final Treatment Visit who completed treatment (as defined below), excluding HCV reinfection.

Virologic failure rate for SVR₁₂ = any subject who experiences **On-treatment virologic failure** or **Relapse₁₂** out of all ITT subjects.

Only subjects who have at least one post-treatment HCV RNA value will be included in analyses of relapse.

Completion of treatment: For the analysis of relapse, completion of treatment is defined as study drug duration of 52 days or greater for Arm A and 77 days or greater for Arm B. If the last available post-treatment value is \geq LLOQ, then the subject will be considered a relapse (i.e., will not require confirmation).

HCV reinfection: HCV reinfection is defined as confirmed HCV RNA \geq LLOQ after the end of active treatment in a subject who had HCV RNA < LLOQ at Final Treatment Visit, along with the post-treatment detection of a different HCV genotype, subtype, or clade compared with baseline, as determined by phylogenetic analysis of the NS3 or NS5A,

and/or NS5B gene sequences. Reinfection in the case of the same HCV subtype is defined as a clade switch, as indicated by the lack of clustering between the baseline and post-treatment sequences by phylogenetic analysis. If phylogenetic analysis is not possible due to technical difficulties, HCV reinfection may be determined with a confirmed HCV genotype or subgenotype switch by the Versant HCV Genotype Inno-LiPA Assay v2.0 or Sanger assay.

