Post-treatment relapse is defined as described earlier (**Relapse₁₂** and **Relapse_{overall}**), and no genotype, subtype, or clade switch compared with baseline as determined by phylogenetic analysis of the NS3 or NS5A gene sequences. If phylogenetic analysis is not possible due to technical difficulties, the subject will be defined as having a post-treatment relapse unless an HCV genotype or subtype switch is confirmed by the Versant HCV Genotype Inno-LiPA Assay v2.0 or Sanger assay.

Reasons for SVR₁₂ Non-Response

Subjects who do not achieve SVR₁₂ (SVR₁₂ non-responders) will be categorized as having:

1. On-treatment virologic failure (see **On-treatment virologic failure** definition);
2. HCV reinfection (see definition described earlier);
3. Relapse₁₂;
4. Prematurely discontinued study drug with no on-treatment virologic failure (defined as any SVR₁₂ non-responder who prematurely discontinued study drug [study drug duration < 52 days for Arm A and < 77 days for Arm B] and did not meet the **On-treatment virologic failure or reinfection** definitions);
5. Missing follow-up data in the SVR₁₂ window (defined as any subject who completed study drug without data in the SVR₁₂ window after applying the imputation rules and not meeting the definitions of [1], [2], [3], or [4]);

6. Other (defined as any SVR₁₂ non-responder not meeting the definitions of [1] – [5]).

For the reasons for SVR₁₂ nonresponse defined above, subjects are only to be counted in 1 category. Specifically, subjects who were SVR₁₂ nonresponders meeting the definition of HCV reinfection will be counted in the reinfection category regardless of whether they meet the definition of prematurely discontinued study drug or relapse₁₂.

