10.7 Additional Efficacy Analyses

The following additional efficacy endpoints will be summarized for the ITT population:

- The percentage of subjects with HCV RNA < LLOQ at each post-baseline visit in the Treatment Period (using data as observed);
- The percentage of subjects with SVR₄;

The percentage of subjects with virologic failure through Post-Treatment Week 12. The number and percentage of subjects meeting each additional efficacy endpoint will be calculated along with a two-sided 95% CI using the Wilson's score method. Imputations for missing data will be performed as described in Section 6.3 for analysis of SVR, virologic failure, and relapse. The first bulleted endpoint above will be presented using data as observed.

A summary of the subjects who completed treatment and relapsed (defined as **Relapse₁₂**) will be prepared displaying the number of subjects relapsing overall and by SVR visit window (within the SVR₄, SVR₁₂ windows or after SVR₁₂ window), including the subject number and the SVR visit window corresponding to the first HCV RNA value of those indicating the occurrence of relapse. A similar summary will be prepared for subjects who prematurely discontinued treatment and relapsed after having HCV RNA < LLOQ at their Final Treatment Visit. A listing of subjects in the ITT population excluded from the relapse denominator (e.g., study drug duration < 52 days for subjects assigned to 8 weeks of treatment, study drug duration < 77 days for subjects assigned to 12 weeks of treatment, or no post treatment HCV RNA) will be provided, as applicable.

A listing of subject numbers and reasons for non-response to SVR₁₂ will be prepared.

The concordance between SVR₄ and SVR₁₂ will be assessed for the overall population (across treatment arms) by the agreement between SVR₄ and SVR₁₂ and the positive predictive value (PPV) and negative predictive value (NPV) of SVR₄ on SVR₁₂. The agreement between SVR₄ and SVR₁₂ is a percentage defined as the number of subjects achieving both SVR₄ and SVR₁₂ and the number of subjects where both SVR₄ and SVR₁₂

are not achieved. The PPV of SVR₄ on SVR₁₂ is the proportion of subjects who achieve SVR₁₂ out of all subjects who achieved SVR₄. The NPV of SVR₄ on SVR₁₂ is the proportion of subjects who do not achieve SVR₁₂ out of all subjects who did not achieve SVR₄.

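### mITT-VF drops early stoppers whose virus returns after treatment but keeps those who are cured, which raises this sensitivity SVR12 by about 1 point per such subject at N=100

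*SAP*

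**What the plan says.** SAP 5.1.2 defines the sensitivity set as "the ITT population modified to exclude subjects who did not achieve SVR₁₂ for reasons other than virologic failure (mITT-VF"). Protocol 8.1 and 8.1.2.3 specify the same set. SAP 10.5 reports it by genotype and overall, with normal-approximation and Wilson intervals, and lists the subjects excluded.

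Who is excluded follows from SAP 10.1:

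- SVR12 is timed from the dose actually taken last: "12 weeks after the last actual dose of active study drug) without any confirmed quantifiable" post-treatment value. There is no minimum treatment duration.
- Virologic failure for SVR12 is on-treatment virologic failure or Relapse12.
- Relapse12 exists only "for a subject with HCV RNA < LLOQ at Final Treatment Visit who completed treatment (as defined below"), where completion means "study drug duration of 52 days or greater for Arm A and 77 days or greater for Arm B".
- Category 4 of the reasons for non-response is "Prematurely discontinued study drug with no on-treatment virologic failure". It takes SVR12 non-responders below those durations who meet neither the on-treatment failure nor the reinfection definition.

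SAP 10.8 names category 4 among the reasons that are not virologic failure. SAP 10.7 plans a separate summary of "subjects who prematurely discontinued treatment and relapsed after having HCV RNA < LLOQ at their Final Treatment Visit".

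**The concern.** Take two subjects who stop on the same early day, both below LLOQ. One is cured and stays in the numerator and denominator of mITT-VF. The other has confirmed quantifiable HCV RNA after treatment and is deleted. The outcome of both was observed, so this is not a missing-data exclusion: the result itself decides who is analysed.

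mITT-VF is the only alternative population planned for SVR12, and SAP 10.5.1 allows no imputation beyond Section 6.3. Its name invites the reader to take it as efficacy with the non-virologic losses removed. A return of virus after a short course is an observed virologic outcome, and the data will exist: Protocol 5.1.2, 5.1.3 and 5.4.1 keep early stoppers in follow-up for HCV RNA for 12 weeks. SAP 10.1 and 10.7 treat the same people evenly in the relapse analysis, where early stoppers leave the denominator whatever their outcome.

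**Working it through.** **The plan's own figure.** SAP 4.3 gives a half-width of 3.3% at 97% SVR12 with N=100. 1.96 × √(0.97 × 0.03 / 100) = 3.34%, which agrees. It serves below as a yardstick; the plan gives no figure for mITT-VF.

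**Notation.**
- S: subjects achieving SVR12
- v: virologic failures as the SAP counts them
- k: early stoppers with post-treatment HCV RNA ≥ LLOQ and neither on-treatment failure nor reinfection
- m: other exclusions (missing outcome, reinfection)
- c: early stoppers who achieve SVR12 (part of S)
- N = S + v + k + m

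**Formulas.**
- As written: S / (S + v)
- Keeping the k subjects as failures: S / (S + v + k)
- Completers only (cured early stoppers dropped too): (S − c) / (S + v − c)

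**Illustration at the planning rate.** S=97, v=1, k=1, m=1:
- As written: 97/98 = 98.98% (Wilson 94.4 to 99.8)
- Keeping the subject: 97/99 = 97.98% (Wilson 92.9 to 99.4)
- Difference: 1.00 point

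**More than one case.** With S=97, N=100 and m=0, keeping the k subjects gives 97.0% throughout. As written:

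| k | mITT-VF | Shift (points) |
|---|---|---|
| 0 | 97/100 = 97.0% | 0 |
| 1 | 97/99 = 98.0% | 0.98 |
| 2 | 97/98 = 99.0% | 1.98 |
| 3 | 97/97 = 100% | 3.00 |

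At S=95 and N=100 the shift runs from 0.96 points (k=1) to 5.0 points (k=5).

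**By genotype.** SAP 4.2 targets about 25 GT3 subjects. With exactly 25, one such GT3 case and no other failure, the figures are 24/24 = 100% as written and 24/25 = 96.0% with the case kept.

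**Against completers only.** With S=97 and N=100, k=1 gives 97.98% as written. The completers-only figure is 96/98 = 97.96% for c=1 and 94/96 = 97.92% for c=3. With k=2 the figures are 98.98% as written, and 96/97 = 98.97% (c=1) to 94/95 = 98.95% (c=3). The shift is 0.01 to 0.06 points.

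**Expected shift, on assumptions.** The documents give neither the all-cause early-stop rate nor the share who rebound. Assume 2% virologic failure among completers, an early-stop share e of 1 to 5%, a rebound share r of 25 to 75%, and no missing data. Then SVR12 with rebounders kept is s = (1 − e) × 0.98 + e(1 − r), and mITT-VF is s / (s + 0.02(1 − e)).
- e=1%, r=25%: 98.02% − 97.77% = 0.25 points
- e=5%, r=75%: 98.03% − 94.35% = 3.68 points

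For context, Protocol Table 3 shows 8/2,265 = 0.4% stopping for an adverse event. That is one cause only, but it makes the lower end more plausible.

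**The case against.** The strongest reply is that the size depends on the comparator. Against a completers-only set, which is the rule the SAP uses for relapse, the shift almost vanishes. The 1-point effect therefore comes mostly from whether a return of virus after a short course should count as virologic failure, and that is a choice of estimand. This stands, and it is why the protocol-defined line should stay. It does not remove the uneven handling of cured and rebounding early stoppers within mITT-VF.

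A second reply is that counting every early stopper with quantifiable RNA would include someone who stopped after a few days and was never suppressed, which is not relapse. This is fair, and it also argues for an added line rather than a replacement.

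Stronger readings that a reader might infer, and that the documents do not support:

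- *All early stoppers with quantifiable RNA are removed.* No. Breakthrough can be confirmed by the final treatment value and the next post-treatment value. RNA ≥ LLOQ at end of treatment, sampled on or after Day 36 with at least 36 days of drug, is end-of-treatment failure. Both are on-treatment failures and stay in.
- *These failures are hidden.* No. The ITT analysis counts them as failures. They appear in the listings of non-response reasons and of mITT-VF exclusions, and those suppressed at the Final Treatment Visit appear in the 10.7 summary.
- *A set that can never fall below ITT must be biased.* This does not discriminate, because the added line also removes only non-responders.
- *The earlier programme shows the size.* It does not. Protocol Table 2 gives 2206/2256 = 97.8% for the pooled naïve and TE-PRS subjects, so 50 lacked SVR12. The Introduction reports "23 subjects experienced virologic failure (2 with GT1, 2 with GT2, and 19 with GT3"), one of them a reinfection, leaving 22. If both counts cover the same set, 50 − 22 = 28 would be excluded, giving 2206/2228 = 99.0%. That gap reflects every exclusion, including missing data. How many of the 28 were rebounds after early stopping is not stated.

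**Conclusion.** The point holds in a limited form. SAP 5.1.2, read with 10.1 and 10.8, makes membership of mITT-VF depend on an observed virologic outcome among early stoppers. Relative to keeping those subjects as failures, the sensitivity SVR12 rises by about 1 percentage point for each one at N=100, against a planned half-width of 3.3 points. A single GT3 case could move that genotype's figure by 4 points. The shift is zero if no early stopper rebounds and at most 0.06 points against a completers-only set in the cases computed.

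The primary ITT SVR12 is not affected, and no hypothesis is tested. The worked counts are illustrations at the planning rate, because the documents do not give the number of such subjects to expect. This is a cheap improvement to one descriptive sensitivity analysis and does not invalidate the plan.

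**What to change.** Keep the mITT-VF line as the protocol defines it, so that comparison with other reports using that definition is preserved. In SAP 5.1.2 and 10.5, add a second line that excludes only (a) reinfections and (b) SVR12 non-responders with no observed virologic outcome after the Section 6.3 imputation. In that line, count as a failure any non-reinfected early stopper whose post-treatment HCV RNA is confirmed, or last available, at ≥ LLOQ. The last-available rule already exists for relapse in SAP 10.1. A footnote giving how many of these subjects were below LLOQ at the Final Treatment Visit would separate rebound from never having been suppressed. Record the addition in SAP 12.1, since Protocol 8.1 and 8.1.2.3 specify only the existing set.

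The cost is one analysis flag and one extra table row, with a slightly lower sensitivity figure if such cases occur. No new visits, samples or changes to the primary analysis are needed.

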5.1.3 Safety Population

All subjects who receive at least one dose of study drug will be included in the safety population. Safety analysis will be performed on the overall population, combining Arms A and B.

6.0 Analysis Conventions

6.1 Definition of Baseline, Final Treatment, and Final Post-Treatment Assessments

6.1.1 Baseline

The baseline value refers to the last non-missing measurement collected before the first dose of study drug is received.

The protocol specifies that all Day 1 assessments are to be performed prior to administering the first dose of study drug. Therefore, all Day 1 assessments will be assumed to be pre-dose and the baseline value will be the last non-missing measurement collected on or before the first day of study drug administration. If multiple measurements that are prior to dosing are recorded on the same date, then the average of these measurements will be considered as the baseline value.

The same baseline value will be used for analyses of the Treatment and Post-Treatment Periods.

Safety assessments that are related to a serious adverse event that occurred on the first dose day are excluded when applying this algorithm.

6.1.2 Study Days

Study Days (Days Relative to the First Dose of Study Drug)

Study days are calculated for each time point relative to the first dose of study drug. Study days are negative values when the time point of interest is prior to the first study drug dose day. Study days are positive values when the time point of interest is after the first study drug dose day. There is no Study Day 0. Study Day 1 is the day of the first dose of study drug.

Study Drug End Days (Days Relative to the Last Dose of Study Drug)

Study drug end days are calculated for each time point relative to the last dose of study drug. The last day of study drug dosing is defined as Study Drug End Day 0. Days before it have negative study drug end days and days after it have positive study drug end days.

Final Treatment Value

The final treatment value is defined as the last non-missing measurement collected after Study Day 1 and on or before Study Drug End Day 2.

Final Post-Treatment Value

The final post-treatment value for each subject is the last non-missing measurement collected after Study Drug End Day 2 and on or before Study Drug End Day 999.

6.2 Definition of Analysis Windows

For efficacy analyses of HCV RNA, the time windows specified in [Table 1](#) and [Table 2](#) describe how efficacy data are assigned to protocol-specified time points during the Treatment and Post-Treatment Periods, respectively. All time points and corresponding time windows are defined based on the date/time of blood sample collection.

For safety laboratory data, PRO data, Child Pugh score and vital sign data, the time windows specified in [Table 1](#) and [Table 3](#) describe how data are assigned to protocol-specified time points.

If more than one assessment are included in a time window, the assessment closest (except in analyses of SVR) to the nominal time will be used. If there are two observations equally distant to the nominal time, the latest one will be used in analyses. For analyses of SVR (e.g., SVR₁₂), the last value in the window will be used.

If multiple measurements are made on the same day for a safety laboratory parameter or a vital sign parameter, the average of the values will be used to calculate descriptive statistics and in analyses of the mean change from baseline. For summaries of shifts from baseline and potentially clinically significant values, multiple values on the same day will not be averaged; all values will be considered for these analyses.

Table 1. Analysis Time Windows for HCV RNA and Resistance Endpoints, Safety Laboratory and Vital Sign Measurements, Child Pugh Scores and PRO Instruments (Treatment Period)

Scheduled Visit	Nominal Day (Study Day)	Time Window (Study Day Range)
Day 1/Baseline ^a	1	≤ 1 ^a
Week 4	28	2 to 42
Week 8	56	43 to 70
Week 12 ^b	84	71 to 98
Final Treatment Visit ^c	2 to ≤ 2 days after last dose of study drug	

a. Day of first dose of study drug.

b. For 12-week treatment duration only.

c. The last value within the window will be used to define the Final Treatment Visit value. The upper bound of this Final window is Study Drug End Day 2. Study Drug End Day 0 is defined as the day of the last dose of study drug.

Note: For all windows, data must be on or before Study Drug End Day 2. The result closest to the scheduled time point will be used. PRO instruments are collected at Day 1 and End of Treatment Visit, which can be at Week 8, or 12 depending on treatment assignment, or Premature Discontinuation Visit.

Table 2. Analysis Time Windows for HCV RNA and Resistance Endpoints (Post-Treatment Period)

Scheduled Visit ^a	Nominal Day (Study Drug End Day)	Time Window (Study Drug End Day Range)
Post-Treatment Week 4	28	3 to 56
Post-Treatment Week 12	84	57 to 126
SVR ₄ ^b	28	3 to 56
SVR ₁₂ ^b	84	57 to 126

a. Post-Treatment Visits are applicable for subjects who received at least one dose of study drug.

b. For SVR windows, the last value in the window will be used.

Note: The result closest to the scheduled time point will be used, except for SVR₄ and SVR₁₂. For all windows, data must occur after Study Drug End Day 2. Study Drug End Day 0 is defined as the day of the last dose of study drug.

Table 3. Analysis Time Windows for Safety Laboratory and Vital Sign Measurements, Child Pugh Scores and PRO Instruments (Post-Treatment Period)

Scheduled Visit ^a	Nominal Day (Study Drug End Day)	Time Window (Study Drug End Day Range)
Post-Treatment Week 4	28	3 to 56
Post-Treatment Week 12	84	57 to 999
Final Post-Treatment Visit ^b	> 2 days after last dose of study drug	

a. Post-Treatment Visits are applicable for subjects who received at least one dose of study drug.

b. The last value within the Post-Treatment Period window will be used to define the Final Post-Treatment visit value. The lower bound of this Final window is Study Drug End Day 3. Study Drug End Day 0 is defined as the day of the last dose of study drug.

Note: The result closest to the scheduled time point will be used. For all windows, data must occur after Study Drug End Day 2. Vital signs are collected at every post-treatment visit; hematology, chemistry and coagulation panels are collected at PTW4 or PT D/C (if subject discontinued prior to PTW4). PRO instruments and Child Pugh Scores are collected at PTW12 (or PT D/C).

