Appendix D. Study Activities – Post-Treatment (PT) Period

Activity	PT Wk 4	PT Wk 12	PT D/C ^a
Vital Signs and Weight	X	X	X
Hematology/Chemistry/Coagulation Panel	X	X ^b	X ^c
Pregnancy Test (urine) ^d	X (u)	X ^e	X (u) ^c
Concomitant Medication Assessment ^e	X	X ^e	X ^e
Child-Pugh Score (cirrhotic subjects only)		X	X
Adverse Event Assessment ^f	X ^f	X ^g	X ^g
HCV RNA Samples	X	X	X
HCV Resistance Sample	X	X	X
Patient Reported Outcomes Instruments (PROs) ^h		X	X
Flow cytometry sample ^h	X	X	X
HIV RNA ⁱ	X	X	X
HCC Screening: Liver Ultrasound ^j		X	X

Wk = Week; PT D/C = Post-Treatment Discontinuation

- Subjects who prematurely discontinue from the Post-Treatment Period should return to the site to complete the PT D/C Visit procedures.
- Chemistry/Coagulation panel will only be collected at PT Wk 12 for subjects in Arm B (compensated cirrhosis).
- Hematology/Chemistry/Coagulation Panel and Pregnancy Test are not required at PT Wk 12, but only at PT D/C if subject discontinues prior to PT Wk 4.
- Women of childbearing potential do not require pregnancy testing beyond PTW4. Pregnancy testing will be performed at PT D/C visit only if the subject discontinues prior to PTW4. Pregnancy testing in PT Period is not required for females of non-childbearing potential as defined in Section 5.2.4.
- Only medications taken for SAEs and treatment of HCV will be collected after 30 days post-dosing.
- Nonserious AEs and all SAEs will be collected until 30 days post dosing. All spontaneously reported SAEs will be collected thereafter. See specific information regarding adverse event collection in Section 6.1.4.

- g. Only SAEs will be collected thereafter as described in Section [6.1.4](#).
- h. PROs should be administered before any study procedures in the order listed in Section [5.3.1.1](#).
- i. For HCV/HIV co-infected subjects.
- j. HCC Screening Liver Ultrasound performed only subjects in Arm B as described in Section [5.3.1.1](#).

Note: Day 1 of the Post-Treatment Period will be defined as the day after the last dose of study drug.

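### For PRO and Child-Pugh data, the End Day 2 cut-off files a completer's late end-of-treatment assessment under Post-Treatment Week 4 and removes it from the end-of-treatment summaries

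*SAP*

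**What the plan says.** SAP section 6.2 gives the analysis windows. The title of Table 1 includes "Child Pugh Scores and PRO Instruments (Treatment Period", and its ranges are Study Days 43 to 70 for Week 8 and 71 to 98 for Week 12. The note below the table limits all of them: "Note: For all windows, data must be on or before Study Drug End Day 2". Footnote c sets the same limit for the Final Treatment Visit: "The upper bound of this Final window is Study Drug End Day 2". Section 6.1.2 repeats it in the general definition of a final treatment value: "on or before Study Drug End Day 2". End Day 0 is the day of the last dose.

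The title of Table 3 includes "Child Pugh Scores and PRO Instruments (Post-Treatment Period", and its Post-Treatment Week 4 row covers End Days 3 to 56.

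On collection, the Table 1 note says "PRO instruments are collected at Day 1 and End of Treatment Visit, which can be at Week 8, or 12 depending on treatment assignment", or at premature discontinuation. The Table 3 note says "PRO instruments and Child Pugh Scores are collected at PTW12 (or PT D/C". Protocol Appendices C and D agree: PROs at Day 1 and EOT, Child-Pugh at Screening and EOT, then both at Post-Treatment Week 12 or post-treatment discontinuation (PT D/C). Neither is marked at Post-Treatment Week 4. The TSQM is not given on Day 1.

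**The concern.** Laboratory and vital-sign data are collected at several on-treatment visits and are due again at Post-Treatment Week 4, so a late EOT visit costs them little. PRO and Child-Pugh are different. Each has one scheduled on-treatment assessment after baseline, so if that value leaves the treatment-period windows nothing can take its place.

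A subject who finished treatment, attended a few days late and was assessed would then be missing from the EOT PRO summaries and the EOT column of the Child-Pugh shift table. The value would appear under a scheduled visit at which it is not collected. For the TSQM it is the subject's only on-treatment score. Protocol section 8.1.3 also names change from baseline to the Final Treatment Visit as a PRO analysis, and that analysis would lose the same subjects.

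**Working it through.** The plan has no figure of its own on this point. The check applies the window rules to an EOT visit held a given number of days after the last dose.

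**Inputs.** Table 1 ranges, its note and footnote c; Table 3 ranges; section 6.1.2; nominal last dose on Study Day 56 (Arm A) or Study Day 84 (Arm B). End Day = visit day − last-dose day.

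| End Day of EOT visit | Arm A Study Day | Arm B Study Day | Treatment-period assignment | Post-treatment assignment |
|---|---|---|---|---|
| 0 to 2 | 56 to 58 | 84 to 86 | Week 8 (A) or Week 12 (B), and Final Treatment | none |
| 3 to 14 | 59 to 70 | 87 to 98 | none, although inside the printed range | Post-Treatment Week 4 |
| 15 to 56 | 71 to 112 | 99 to 140 | none | Post-Treatment Week 4 |
| 57 and later | 113 and later | 141 and later | none | Post-Treatment Week 12 |

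Example, Arm A: last dose Day 56, EOT visit Day 60. End Day = 60 − 56 = 4, so the SF-36v2, EQ-5D-3L and TSQM go to Post-Treatment Week 4, and there is no Week 8 or Final Treatment value.

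Example, Arm B: last dose Day 84, EOT visit Day 88. End Day = 88 − 84 = 4, so the EOT Child-Pugh category is missing. SAP section 11.5 leaves missing post-baseline values out of the percentages.

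With dosing on schedule, the printed ranges can be used only to Day 58 and Day 86. The days cut are 70 − 58 = 12 and 98 − 86 = 12, which are End Days 3 to 14 in each arm.

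**Is there another rule that returns the value?** No SAP rule assigns these data by visit label.

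**Size.** The documents give no rate of late visits, so the rate r is an assumption. Subjects lost = r × 100 for PRO and r × 20 for Child-Pugh (planned Arm B). Inflation of the standard error of a mean PRO change = 1/√(1 − r) − 1, assuming the spread of the scores is unchanged.

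| r (assumed) | PRO, of about 100 | Child-Pugh, of about 20 | Standard-error inflation |
|---|---|---|---|
| 2% | 2 | 0.4 | 1.0% |
| 5% | 5 | 1 | 2.6% |
| 10% | 10 | 2 | 5.4% |

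**The case against.** The cut-off has a sound basis. Protocol section 1.3 ends the Treatment Period at the last dose, and Appendix D adds: "Note: Day 1 of the Post-Treatment Period will be defined as the day after the last dose of study drug". The SAP therefore already allows two days beyond the protocol's own boundary. For premature discontinuation, protocol section 5.4.1 asks for the visit within two days of the final dose, which is the same limit. The Post-Treatment Week 4 row is not idle for these data either, because a PT D/C visit, with PRO and Child-Pugh, can fall on End Days 3 to 56. The SAP outputs concerned are descriptive PRO summaries (10.9) and a shift table (11.5).

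All of this stands. It justifies the cut-off as a definition and settles the case of premature discontinuation. It does not settle the completer's case: the documents set no limit in days for that EOT visit, so one held on End Day 4 is not a stated deviation, yet its only on-treatment value is moved out of end of treatment.

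Three stronger readings are tempting and are not supported.

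- A reader might infer from the ranges ending at Days 70 and 98 that late off-drug visits were meant to count. But Days 42 and 70 are the midpoints of the nominal days ((28 + 56)/2 and (56 + 84)/2), and Day 98 is 84 + 14. The ranges also serve Arm B subjects still on drug at Week 8 and subjects whose dosing runs late.
- A reader might assume visit times spread normally about the last-dose day with a standard deviation of 2 to 4 days, which gives 11% to 27% late. Nothing in the documents supports that spread.
- A reader might conclude that the value is lost altogether. It can still count in the section 10.9 summary of improvement at any time up to a timepoint, or serve as the Final Post-Treatment value if nothing later exists.

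**Conclusion.** The point holds for completers, for PRO instruments and Child-Pugh only. An EOT assessment on End Days 3 to 56 leaves the Week 8 or 12 and Final Treatment summaries and the EOT shift table, and no other scheduled value replaces it. This follows from the SAP text without assumption.

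The number affected is unknown. The range of 2 to 10 subjects for PRO and 0.4 to 2 for Child-Pugh rests wholly on the assumed 2% to 10% rate and the planned 100 and 20 subjects. SVR₁₂, on-treatment virologic failure and relapse are untouched. This is a minor, inexpensive correction, best made before data lock so that late EOT values are not handled ad hoc.

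**What to change.** In SAP Table 1 and section 6.1.2, for PRO instruments and Child-Pugh only:

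1. Assign assessments recorded at the EOT visit to Week 8 or Week 12 and to Final Treatment by visit label, up to the printed Day 70 and Day 98 limits (End Day 14 when dosing ends on schedule).
2. Keep the Post-Treatment Week 4 row of Table 3 for PT D/C assessments only. Deleting the row would leave some PT D/C values without a visit window. A plain extension to End Day 14 would, under the last-value rule for Final Treatment, let a PT D/C value replace an on-time EOT value. The visit label prevents both.
3. Compute the EOT Child-Pugh score from the bilirubin, albumin and INR drawn at that same visit, since the laboratory windows do not move.
4. State how a premature-discontinuation assessment made after End Day 2 is reported; it is already outside the protocol's timing.

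Leave the HCV RNA, laboratory and vital-sign windows as they are.

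The cost is SAP wording and a change to the window programming, with no new data. The downside is that some Final Treatment values will have been taken up to two weeks after the last dose; their number and timing should be footnoted.
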